## 5.3 Diagnostic, Pre-, Peri- and Post-Intervention Variables

Following diagnostic variables will be collected and described:

- Time between diagnostic radiology and treatment (hours)
- Type of radiology (CT, angiography)
- Clinical presentation of PE (e.g. hypotension, syncope, cardiac arrest) (yes, no)
- Distribution of PE (unilateral, bilateral, saddle)
- Cardiac arrest before treatment (yes, no)
- ROSC before treatment (yes, no)
- Cardiac arrest during treatment (yes, no)
- Cardiac arrest after treatment (yes, no)
- ECMO initiated before treatment (yes, no)
- ECMO initiated during treatment (yes, no)
- ECMO initiated after treatment (yes, no)
- Extracorporeal cardiopulmonary resuscitation (ECPR) (yes, no)

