### 3.1 Inclusion/Exclusion Criteria

Eligible patients are all adult patients ( $\geq 18$  years) who have been treated with FlowTriever® or thrombolysis for acute PE verified by computed tomography pulmonary angiography (CTPA) or angiography, during the time period from January 1st of the year when FlowTriever® was introduced at each respective participating center, to the end of 2023.

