## 5.6 Confounders and Predictors

The confounders and predictors for the outcomes will be used in propensity scores and adjustments. All variables listed below will be included when building propensity scores. For the adjusted analyses, only the

strongest confounders and predictors will be part of the analyses. The number of confounders/predictors in the adjusted analyses will be based on the number of events available in the studied cohort. The general recommendation is to not have more than 1 variable/10 events in a statistical model. We will calculate the maximum number of variables in our study as N events/10.

The following variables will be investigated whether they are statistically defined confounders, i.e. related to both the intervention and the outcome:

- Contraindication for thrombolysis (8 categories)
- Insufficient previous effect of thrombolysis
- Cardiac arrest before treatment

The following variables will be investigated for their relation to the study outcomes:

- Age
- Sex
- Active cancer
- Invasive ventilation before treatment
- Circulatory instability
- Chronic heart failure
- Chronic pulmonary disease (COPD, asthma, other)
- Respiratory rate >30 beats/min
- Center

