## 6 Statistical Methods

### 6.1 Sample Size

The few non-industry sponsored studies have been performed on a limited number of patients. Furthermore, there is an insufficiency of data concerning the outcomes in this particularly severe group of patients, making it challenging to make informed assumptions for a sample size calculation.

During the planned inclusion period, we anticipate enrolling 60 patients who will undergo the FlowTriever® procedure and 200 patients who will receive thrombolysis intervention. Assuming these group sizes and a 40% incidence rate of the composite outcome in the thrombolysis group, with a two-sided Fisher's exact test and an alpha level of 0.05, the FlowTriever® group would need to demonstrate a 50% reduction, equivalent to a 20% incidence of the composite outcome, to achieve a minimum of 80% statistical power. Our evaluation indicates that achieving such an outcome is feasible within the scope of this study, making it a viable candidate for a positive outcome.

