## 6.7 Subgroup Analyses

The investigation of interaction with the intervention group will be performed on following subgroup variables:

- ECMO treatment before, during and after the intervention (yes vs no)
- Cardiac arrest before and during intervention (yes vs no)

These analyses will only be performed if the number of events is at least 10 in each cell.

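### ROSC before treatment is recorded but never used, so the yes/no arrest covariate pools ongoing arrest with restored circulation and leaves residual confounding if those patients are unevenly split between the groups

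*SAP*

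**What the plan says.** - **Eligibility (SAP 3.1).** "Eligible patients are all adult patients ( $\geq 18$ years) who have been treated with FlowTriever® or thrombolysis for acute PE", provided the embolism was verified by CT pulmonary angiography or angiography. There is no condition on circulatory status at treatment. Section 3 keeps suspected but unverified embolism out of the comparisons, and section 4.1 puts all treated patients in the full analysis set.
- **Data collected (SAP 5.3).** Arrest before treatment is one item and "ROSC before treatment (yes, no" is another. ECMO before, during and after treatment, and ECPR, are also recorded.
- **Adjustment (SAP 5.6).** The list has one arrest item, "Cardiac arrest before treatment", and it is a candidate to be tested as a confounder. ROSC, ECMO and ECPR are not listed. The same list supplies the propensity score.
- **Analyses (SAP 6.5).** The primary analysis is logistic regression adjusted for known and statistically identified confounders. The sensitivity analyses are propensity score adjustment and 1:1 matching.
- **Subgroups (SAP 6.7).** "Cardiac arrest before and during intervention (yes vs no" is one of two subgroup variables, run only with at least 10 events in each cell. ROSC plays no part.

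**The concern.** Recording ROSC separately shows that the plan recognises two kinds of patient with arrest before treatment. They can be expected to differ widely in prognosis, and death at 30 days is one of the two components of the primary composite. A yes/no arrest item makes them exchangeable. Adjusting for it, or matching on a score that contains it, can pair a patient with restored circulation in one group with a patient still in arrest in the other.

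The bias depends on how patients without ROSC are divided between the groups. If most are in the thrombolysis group, the estimate moves towards FlowTriever, which is the direction of the hypothesis in section 2. If the shares among arrested patients are equal, there is no bias from this source. If FlowTriever has the larger share, the estimate moves against it. Both planned sensitivity analyses draw on the same list as the primary model, so neither can reveal the problem.

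**Working it through.** **1. The plan's own figure.** Inputs from SAP 6.1: "60 patients who will undergo the FlowTriever® procedure and 200 patients who will receive thrombolysis intervention"; "40% incidence rate of the composite outcome in the thrombolysis group"; FlowTriever "equivalent to a 20% incidence of the composite outcome"; two-sided Fisher's exact test at "an alpha level of 0.05". Exact enumeration over all outcomes gives a power of 82.7%. This agrees with the stated minimum of 80%, so no stated figure is in dispute. The planned effect is an odds ratio of (0.20/0.80)/(0.40/0.60) = 0.375.

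**2. Worked example with no true treatment effect.** The documents give no arrest share, ROSC share or risk by ROSC status. The splits below are assumptions, chosen so that thrombolysis reproduces 40%.

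| | Arrest, no ROSC (risk 90%) | Arrest, ROSC (risk 50%) | No arrest (risk 32.5%) | Events |
|---|---|---|---|---|
| Thrombolysis, 200 | 20 | 20 | 160 | 18 + 10 + 52 = 80 (40%) |
| FlowTriever, 60 | 0 | 12 | 48 | 0 + 6 + 15.6 = 21.6 (36%) |

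- Crude odds ratio: (21.6/38.4)/(80/120) = 0.84.
- Arrest stratum: FlowTriever 6/12, thrombolysis 28/40, odds ratio (6/6)/(28/12) = 0.43. No-arrest stratum: odds ratio 1.
- Mantel-Haenszel, stratified on arrest yes/no: (6×12/52 + 15.6×108/208)/(6×28/52 + 32.4×52/208) = (1.385 + 8.1)/(3.231 + 8.1) = 0.84.

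Here stratifying on the yes/no item removes essentially none of the bias.

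The result depends on the FlowTriever column. If 3 of its 12 arrests were without ROSC at the same 90%, arrest-stratum events become 9×0.5 + 3×0.9 = 7.2. The pooled odds ratio is then (7.2×12/52 + 8.1)/(4.8×28/52 + 8.1) = 9.762/10.685 = 0.91. With 6 of 12, the same share as in thrombolysis, it is 1.00.

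**3. Range under other assumptions.** This uses expected-data logistic regression on treatment and arrest yes/no, with no treatment effect within ROSC strata and the same arrest share in both groups. Half of arrested thrombolysis patients and no FlowTriever patients are without ROSC. Composite risks (no arrest / ROSC / no ROSC) are 25/50/90% in set A and 30/50/80% in set B. The implied thrombolysis incidence runs from 29.5% (set A, 10% arrest: 0.9×0.25 + 0.1×0.70) to 40.5% (set B, 30% arrest: 0.7×0.30 + 0.3×0.65). The bracketed figure is the chance of a false significant FlowTriever benefit, nominally 2.5%.

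| Arrest share | Set A | Set B |
|---|---|---|
| 10% | 0.90 (5.0%) | 0.93 (4.1%) |
| 20% | 0.81 (8.9%) | 0.87 (6.4%) |
| 30% | 0.73 (14.7%) | 0.81 (9.6%) |

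Other splits of the share without ROSC among arrested patients (thrombolysis vs FlowTriever), over the same grid:

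- a quarter vs none: 0.86 to 0.97
- half vs half: 1.00
- a quarter vs half: 1.04 to 1.16

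**4. Precision after exclusion.** If *n* thrombolysis patients at an assumed 90% event rate are removed, the incidence is (80 − 0.9*n*)/(200 − *n*). With FlowTriever held at 60 patients and 20%:

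| Removed | Thrombolysis incidence | Fisher power |
|---|---|---|
| 0 | 40% | 82.7% |
| 10 | 71/190 = 37.4% | 70% |
| 20 | 62/180 = 34.4% | 55% |
| 30 | 53/170 = 31.2% | 35% |

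**The case against.** **The split is unknown.** A reader might infer that patients without ROSC sit mostly in the thrombolysis group, and that thrombolysis is therefore charged with deaths that have nothing to do with the choice of treatment. This is plausible for an intravenous drug compared with a catheter procedure, but the documents do not support it as a statement of fact. They give no count by group. They also record ECPR and ECMO before and during treatment, so FlowTriever patients without ROSC are possible. This objection stands, and the direction of bias must stay conditional.

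**Imaging verification already filters.** Patients treated on suspicion during an arrest who were never imaged are outside the comparisons. Those imaged later had to survive long enough for it, which argues for fewer such patients and a lower event rate than assumed. This stands in part: patients imaged before the arrest, or verified afterwards, remain.

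**Other covariates act as proxies.** The circulatory instability and invasive ventilation items are in the 5.6 list and enter the propensity score. However, the first is undefined, the second does not separate ROSC from no ROSC, and the adjusted model keeps only the strongest variables. The help is partial.

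**The arrest subgroup covers it.** It pools arrest before and during the intervention and ignores ROSC. In the worked example the FlowTriever arrest cell has 6 events, below the required 10, so it would not run.

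**The size may be small.** An odds ratio of 0.93 is minor beside the planned 0.375, and the 0.43 above comes from one stratum of an assumed table that matches no planned primary estimate. Both points are fair. The pooled figures are the ones to use.

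**Conclusion.** The gap is in the text: ROSC is collected, and no restriction, covariate, propensity score or subgroup uses it. The primary analysis and both of its sensitivity analyses therefore share a source of residual confounding that they cannot detect.

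Its presence and direction depend on an imbalance that the documents do not show. If patients without ROSC are in the thrombolysis group only, as half of its arrests, and arrest shares are 10% to 30%, the spurious odds ratio is about 0.73 to 0.93, with a 4% to 15% chance of a false FlowTriever benefit. With equal shares there is none, and with the reversed imbalance examined the odds ratio is 1.04 to 1.16. All of these rest on assumed arrest shares, ROSC shares and risks. The finding is that the plan leaves this source of bias open, not that it is known to favour FlowTriever. The change is worth making because the variable is already collected and, in a retrospective study, an exclusion chosen after seeing results would carry less weight.

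**What to change.** 1. **Section 5.6.** Replace the yes/no arrest item with a three-level one (no arrest, arrest with ROSC before treatment, arrest without ROSC before treatment), for both the adjusted model and the propensity score. Report its distribution by group.
2. **Section 6.5.** Pre-specify a sensitivity analysis of the primary composite and of 30-day death that excludes, in both groups, patients in arrest without ROSC before treatment. Report it in Tables 4.1 and 5.1.
3. **Description.** Describe the excluded patients by group, including ECMO and ECPR status, so that a reader can see whether the exclusion also removes very sick FlowTriever patients.

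**Cost.** No new data are needed and the full analysis set is unchanged. The three-level item uses one more degree of freedom; at the planning rates there are 80 + 12 = 92 events, so the plan's own limit is about 9 variables. If one group has nobody in the no-ROSC level, the propensity model cannot estimate that level, and the exclusion analysis becomes the one to rely on. Precision in that analysis falls: under the assumptions in the working, power goes from about 83% to between 70% and 35% when 10 to 30 thrombolysis patients are removed. It should therefore be read by its estimate and confidence interval, not by significance.

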## 5.4 Intervention

Following variables related to the intervention of FlowTriever® will be summarized:

- Indication for intervention (e.g. contraindication to thrombolysis, unsuccessful thrombolysis, other indication)
- Contraindication to thrombolysis (none, trauma, surgery, ischemic stroke, hemorrhagic stroke, active bleeding, risk for bleeding, ongoing anticoagulation, other indication)
- Use of Cellsaver/FlowSaver™ or equivalent
- Rescue treatment after intervention (thrombolysis, surgical embolectomy, ECMO)
- ECMO during intervention (yes, no)
- Technical success (yes, no), defined as achievement of desirable catheter positioning, as assessed by the interventionist
- Procedural success (yes, no), defined as technical success with successful extraction of thrombus material in the absence of major complications, as assessed by the interventionist

- Clinical success (yes, no), defined as hemodynamic or respiratory improvement following intervention, including but not limited to: increase in SaO2, reduced FiO2, regress of hypotension/tachycardia/tachypnoea, reduced need for circulatory support.
- Complications during intervention (bleeding, perforation, other complication)
- Other complications (coded by ICD-10 if relevant)

Following variables related to the treatment with thrombolysis will be summarized:

- Dose of thrombolysis
- Duration of infusion of thrombolysis
- Reason for premature discontinuation of thrombolysis (when relevant)
- Contraindication for thrombolysis (if relevant)
- Rescue treatment after thrombolysis (surgical embolectomy, ECMO)

## 5.5 Outcome Variables

### 5.5.1 Primary Outcome Variable

The primary variable in this study is the composite endpoint death at 30 days and/or severe bleeding (according to GUSTO bleeding criteria) within 7 days after treatment with the FlowTriever® device or contemporary thrombolysis.

### 5.5.2 Secondary Outcome Variables

The secondary variables in this study are:

- Difference in RV/LV-ratio as compared (up to 48h) before, and (up to 48h) after, treatment. RV/LV-ratio before treatment will be assessed on CT, and after treatment on echocardiography.
- Difference in pulmonary artery pressure (systolic, diastolic and mean) as compared (up to 48h) before and (up to 48h) after treatment.
- Incidence of severe bleeding (according to GUSTO bleeding criteria) within 7 days after treatment
- Type of bleeding (severe, moderate, mild GUSTO)
- Intracranial bleeding (yes, no)
- Incidence of all-cause death at 30 days after treatment
- Time to all-cause death within 30 days after treatment
- Causes of death in patients treated with FlowTriever® vs thrombolysis
- Occurrence of cardiac arrest before (within 24 hours), during, or after (within 24 hours) treatment
- Occurrence of rescue treatment with thrombolysis, ECMO, or surgical thrombectomy
- Length of stay in ICU or IMU (hours)
- Length of hospital admission (days)

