## 5 Study Variables

### 5.1 Baseline Characteristics Variables

Following baseline characteristics will be collected and described:

- Age
- Sex (male, female)
- Mechanical ventilation (yes, no)
- Maximum heart rate (0-24 hours before intervention)
- Minimum systolic blood pressure (0-24 hours before intervention)
- Maximum respiratory frequency (0-24 hours before intervention)
- Maximum lactate levels (0-24 hours before intervention)
- Maximum cardiac troponin levels (0-24 hours before intervention)
- Maximum NT-proBNP levels (0-24 hours before intervention)

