### 6.2 General Methodology

Descriptive statistics will be used for group characteristics and outcomes. Mean, standard deviation, median, and range will be described for the continuous variables and frequency and percentage for categorical variables. Intergroup comparisons considering baseline characteristics will be done using Fisher's exact test for

dichotomous variables, Chi-square test for non-ordered categorical variables, and the Mann-Whitney U-test for continuous variables.

The comparative analyses between the groups considering the dichotomous study outcomes will be performed using logistic regression adjusted for known and statistically identified confounders (variables that are related both to the study group and the outcome). Odds-ratios (OR) with associated 95% CI, p-values and area under the receiver operating characteristic curve (AUC-ROC) will be presented. Hosmer-Lemeshow test will be performed as a goodness-of-fit test.

The comparative analyses between the groups considering the continuous study outcomes will be performed using linear regression adjusted for known and statistically identified confounders. Model assumptions will be checked by reviewing diagnostic plots, and if needed transformation (e.g. log) of the outcome variable will be performed. Least square means with associated 95% CI, p-values and  $R^2$  will be presented.

Outcome variables length of stay in ICU (hours) and length of hospital admission (days) will be handled as continuous variables in the case of no censored patients. In case of censored patients in the database, time to discharge will be studied using Cox proportional hazard model, resulting in hazard ratios (HR) with 95% CI and p-value. Proportional hazards assumptions will be checked graphically. Otherwise, the variables will be studied as continuous variables using either linear regression assuming normal distribution if applicable or Poisson or negative binomial regression depending on the distribution of the variables. Results from the Poisson and negative binomial regression result in risk ratio (RR) with 95% CI and p-value.

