Time to all-cause mortality will be investigated by using Cox proportional hazard model, describing HR with 95% CI and associated p-value following adjustment. Event rates, the number of events divided by total number of follow-up time will be described, together with the 95% CI obtained using exact 95% Poisson confidence limits. Graphically, this variable will be described applying Kaplan-Meier technique.

The confirmatory analyses will be performed for the following outcome variables, applying Bonferroni-Holm adjustment to minimize the Type I error:

- The primary composite outcome variable, death at 30 days and/or severe bleeding (according to GUSTO bleeding criteria) within 7 days after treatment
- The secondary outcome variable all-cause death at 30 days post-intervention
- The secondary outcome variable severe bleeding (according to GUSTO bleeding criteria) within 7 days after intervention
- The secondary outcome variable difference in RV/LV-ratio as compared before and after treatment

Additionally, the sensitivity analyses will be conducted applying adjustment for propensity score (PS) and PS 1:1 matching for the confirmatory analyses listed above, using the patients' background data to estimate the PS, performed by using logistic regression. Matching will be made applying nearest neighbour matching with the optimal caliper width of 0.2 of the standard deviation of the logit of the PS, as recommended. The performance will be validated by comparing the patient characteristics between the matched groups, that are expected not to differ, and described by standardized mean difference. The potential selection bias in the PS 1:1 matching will be examined in a drop-out analysis comparing included vs excluded FlowTriever® cases.

All non-confirmatory analyses will be evaluated in an exploratory manner at significance level of 0.05. All analyses will be performed using SAS software version 9.4 or later (SAS Institute Inc., Cary, NC, USA).

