## 6.4 Handling of Missing Data

Missing data for the main study outcomes is not expected. Hence no imputation of missing data is pre-planned.

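### The confirmatory RV/LV change from CT to echocardiography should also be analysed with baseline RV/LV as a covariate, which the SAP does not name

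*SAP*

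**What the plan says.** - **Outcome.** Section 5.5.2 defines "Difference in RV/LV-ratio as compared (up to 48h) before, and (up to 48h) after, treatment" and adds that "RV/LV-ratio before treatment will be assessed on CT, and after treatment on echocardiography".
- **Status.** Section 6.2 lists among the four Bonferroni-Holm outcomes "The secondary outcome variable difference in RV/LV-ratio as compared before and after treatment". Section 3 describes the study as retrospective and observational.
- **Model.** Under section 6.2, continuous outcomes are "performed using linear regression adjusted for known and statistically identified confounders". The propensity score is built from the patients' background data, which section 6.2 does not itemise.
- **Named variables.** Section 5.1 opens with "Following baseline characteristics will be collected and described". Its list has vital signs, lactate and cardiac biomarkers but not RV/LV. Section 5.6 says "All variables listed below will be included when building propensity scores" and names twelve variables, again without RV/LV. For the adjusted models it says "We will calculate the maximum number of variables in our study as N events/10".
- **Missing data.** Section 6.4 says "Missing data for the main study outcomes is not expected" and plans no imputation.

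**The concern.** Analysing a change without its baseline value fixes the slope of the post-treatment value on the pre-treatment value at 1. Here the two values come from different imaging methods, and nothing in the SAP gives a reason for that slope. Treatment was chosen clinically, and section 5.6 itself lists candidate confounders such as contraindication to thrombolysis and cardiac arrest, so equal baseline RV/LV in the two groups cannot be presumed.

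If the slope is below 1 and the groups differ at baseline, the group with the higher CT ratio can appear to fall more with no difference in treatment effect. RV/LV can carry a confirmatory claim. With only one model planned, a reader could not see whether that claim depends on how baseline is handled.

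A related gap is that a patient who dies before the echocardiogram, or has none within 48 hours, has no value. The SAP does not say to whom the RV/LV estimate applies.

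**Working it through.** **The plan's own figures.** The SAP gives no SD, slope, imbalance, number measured or power for RV/LV, so there is no figure to reproduce. Its only power statement (section 6.1: 20% vs 40%, 60 vs 200 patients, Fisher's exact test) concerns the primary composite. It reproduces at 82.7% and does not bear on this point.

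**Step 1: the identity.** In the same patients with the same confounders, let T be the group coefficient for post-treatment echo RV/LV and D the group coefficient for baseline CT RV/LV. Let b be the fitted slope of echo on CT.

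- Change-score contrast = T - D
- Baseline-adjusted contrast = T - b*D
- Change score minus adjusted = (b-1)*D

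This is exact for least squares. A check on simulated data with three confounders gave -0.08633 both ways.

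**Step 2: which contrast is biased.**

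- Case A: with no treatment difference, patients with the same CT baseline have the same expected echo value. The change score is then biased by (b-1)*D.
- Case B: the imbalance D carries over unchanged to the echo scale. The adjusted model is then biased by (1-b)*D.

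**Step 3: illustration.** From the SAP: 60 and 200 patients (section 6.1) and a first Holm step of 0.05/4 = 0.0125. Assumed, with no source in the SAP: within-group SD 0.35 at both times, b = 0.3 to 0.7, D = 0.05 or 0.10, everyone measured, no treatment effect.

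- SE of change score = 0.35*sqrt(2(1-b))*sqrt(1/60+1/200). At b = 0.3 this is 0.35*1.183*0.1472 = 0.061.
- SE of adjusted model = 0.35*sqrt(1-b^2)*sqrt(1/60+1/200)*sqrt(VIF), with VIF = 1 + p(1-p)(D/0.35)^2 and p = 60/260. VIF is 1.004 at D = 0.05 and 1.014 at D = 0.10.
- Rejection rate = two-sided normal probability at 0.0125 (critical value 2.498), shifted by |1-b|*D/SE.

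| D | b | Size of gap | Case A: change score | Case B: adjusted model |
|---|---|---|---|---|
| 0.05 | 0.3 | 0.035 | 2.8% | 3.8% |
| 0.05 | 0.5 | 0.025 | 2.4% | 2.7% |
| 0.05 | 0.7 | 0.015 | 1.9% | 2.0% |
| 0.10 | 0.3 | 0.070 | 8.9% | 13.9% |
| 0.10 | 0.5 | 0.050 | 6.4% | 8.3% |
| 0.10 | 0.7 | 0.030 | 4.1% | 4.6% |

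The nominal rate is 1.25%. With half the patients measured (30 and 100), the ranges are 1.6-4.6% in Case A and 1.6-6.7% in Case B. Simulation (4000 runs per setting) agreed: the unbiased model of each case rejected in 0.9-1.6% of runs.

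**Step 4: precision and measurement error.** The variance ratio, adjusted to change score, is VIF*(1+b)/2. It runs from 0.652 (b = 0.3, D = 0.05) to 0.862 (b = 0.7, D = 0.10), so the adjusted variance is 14-35% lower.

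If CT reliability is 0.8 (an assumption), error in the CT baseline leaves residual confounding of b*(0.2/0.8)*D in the adjusted model. At D = 0.10 that is 0.0075 (b = 0.3) to 0.0175 (b = 0.7).

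**The case against.** **The choice between the two models is open.** A reader might infer that the change score is wrong and that baseline adjustment corrects it. The SAP does not support that. It contains nothing that decides between Case A and Case B. Two modalities make a slope of exactly 1 and an unchanged carry-over of D less natural, but exclude neither. In every row of the table the adjusted model in Case B does somewhat worse than the change score in Case A. With CT reliability 0.8, b = 0.7 and D = 0.10, the true slope is 0.7/0.8 = 0.875. The change score is then biased by (0.875-1)*0.10 = -0.0125 and the adjusted model by +0.0175. At b = 0.3 and 0.5 the change score remains the more biased. This objection stands, and it is why both models should be reported.

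**The magnitude is assumed throughout.** If echo values vary more than CT values, b can reach 1, where the gap vanishes, or exceed it, where the gap changes sign. With no residual imbalance there is no gap. The 0.0125 threshold applies only if RV/LV has the smallest of the four p-values. This also stands.

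**The wording is not closed.** The reference in section 6.2 to known confounders, and its reference to background data for the propensity score, do not exclude baseline RV/LV. The fair statement is that it is not named. A confirmatory test should still not depend on how those phrases are read. The cap in section 5.6 could be read as one study-wide number, so it is ill suited to a continuous outcome rather than meaningless.

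**Missing data.** Section 6.4 speaks of main outcomes and may not be meant to cover a secondary one. In that case RV/LV has no stated missing-data rule at all. Verification of PE by angiography (section 3.1) does not show that a patient lacked a CT, so nothing here rests on that.

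**Conclusion.** The point holds as a cheap improvement of minor severity. A confirmatory outcome in a non-randomised comparison is a CT-to-echo change, and its baseline value is not named as a covariate or a propensity-score variable. The dependence on baseline, (b-1)*D, is exact, but its size in this study is unknown. The 1.9-8.9% and 2.0-13.9% rejection rates are illustrations under the stated assumptions and are not predictions. What can be said is that neither model is safe in both cases, and that planning only one of them would hide the dependence. The primary composite is not affected.

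**What to change.** **Section 6.2, for RV/LV:**

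- Add a linear regression of post-treatment echo RV/LV on group, baseline CT RV/LV and the planned confounders. Make baseline a fixed covariate outside the events-based cap of section 5.6.
- State before analysis which of the two models carries the Holm test, and report the other beside it.
- Rest a confirmatory RV/LV claim only on a result whose direction and conclusion hold in both models.
- Report baseline CT RV/LV by group.
- In the propensity-score analyses of this outcome, put baseline CT RV/LV in the outcome model and keep the single planned score.

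**Section 6.4, for RV/LV:** report by group the number with both measurements. State that the estimate applies to patients alive and measured.

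**Cost.** This takes SAP wording and one covariate that the change score already requires. It loses no further patients and needs no second propensity score or matched set. The downsides are slight variance inflation (VIF up to 1.014 on the assumed inputs), possible residual confounding from error in the CT baseline, and a stricter condition for claiming an RV/LV effect.

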## 6.6 Secondary Analyses

The secondary analyses will be performed applying the general methodology presented above.

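### Cardiac arrest before treatment is counted within a secondary outcome, and the subgroups in 6.7 include events after treatment start (minor; exploratory analyses only)

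*SAP*

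**What the plan says.** Section 5.5.2 of the SAP includes among the secondary outcomes "Occurrence of cardiac arrest before (within 24 hours), during, or after (within 24 hours) treatment". Section 5.6 names "Cardiac arrest before treatment" as a candidate confounder and states that "All variables listed below will be included when building propensity scores". For the adjusted models it says that only the "strongest confounders and predictors will be part of the analyses", up to one variable per ten events, and it gives no threshold for choosing them.

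The arrest outcome is to be compared between groups. Section 6.6 says "The secondary analyses will be performed applying the general methodology presented above", and section 6.2 says "The comparative analyses between the groups considering the dichotomous study outcomes will be performed using logistic regression adjusted for known and statistically identified confounders".

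Section 6.7 names two subgroup variables for interaction with treatment: "ECMO treatment before, during and after the intervention (yes vs no" and "Cardiac arrest before and during intervention (yes vs no". These analyses run only with at least 10 events in each cell. Tables 4.2 and 5.2 in section 7 apply them to the primary and secondary outcomes.

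Section 5.3 records arrest and ECMO before, during and after treatment as separate yes/no items. Neither the arrest outcome nor the subgroup analyses are among the four confirmatory analyses in section 6.2. All other tests are exploratory, at the 0.05 level.

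**The concern.** There are two faults of the same kind: events are placed on the wrong side of the start of treatment.

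- **Outcome.** An arrest before treatment describes how ill the patient was on arrival. Counted as an outcome, it mixes case mix with what happened after treatment. Treatment was not randomised and case mix may well differ between the groups, so the result could favour either one with no effect present. Even with equal case mix, events that treatment cannot change pull the odds ratio towards 1.
- **Subgroups.** ECMO during or after treatment and arrest during treatment can be consequences of treatment, and they overlap with secondary outcomes in 5.5.2 (arrest, rescue ECMO). Patients who reach such a stratum under one treatment need not be comparable with those who reach it under the other. An interaction can then appear although the treatment effect does not differ by patient type.

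**Working it through.** **Inputs from the SAP.** Section 6.1 gives 60 FlowTriever and 200 thrombolysis patients and composite rates of 20% and 40%. Section 6.7 gives 10 events per cell. Section 5.6 gives events/10 covariates. The SAP has no figure for cardiac arrest, so none can be reproduced. Its power statement is not in dispute and reproduces at 82.7% (two-sided Fisher's exact test, 20% vs 40%).

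**Assumptions.** All arrest rates below are assumed. The three periods are combined into one yes/no outcome, prior and later arrest are independent, and all prior arrests fall in the 24 h window. Then

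combined risk = 1 − (1 − prior)(1 − later).

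**1. Imbalance, no true effect (later arrest 8% in both groups, OR 1.00).**

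- Prior arrest 20% thrombolysis, 10% FlowTriever: 1 − 0.80×0.92 = 0.264 and 1 − 0.90×0.92 = 0.172. OR = (0.172/0.828)/(0.264/0.736) = 0.58.
- Prior arrest 20% and 15%: 0.264 and 1 − 0.85×0.92 = 0.218. OR = 0.78.

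Probability of p<0.05 (exact binomial enumeration, Wald test of the log odds ratio): 28% and 9% unadjusted. For later arrest alone (8% vs 8%) it is 3%.

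**2. With the planned adjustment.** Expected events in the first scenario are 200×0.264 + 60×0.172 = 63, so the events/10 rule allows 6 covariates and there is room for prior arrest. If it is in the model, every patient with prior arrest has the outcome by definition, so the treatment odds ratio comes from patients without prior arrest and is unbiased here. Suppose prior arrest enters only when its imbalance between groups has Fisher p<0.05 (simulated studies):

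| Prior arrest | Enters model | Rejection, unadjusted | Rejection, with selection | Rejection, always adjusted |
|---|---|---|---|---|
| 20% vs 10% | 41% | 28% | 6% | 3% |
| 20% vs 15% | 11% | 9% | 4% | 3% |

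In the 59% of studies in the first row where it stays out, the median OR is 0.68 and rejection is 8%. At selection thresholds of 0.10 and 0.20, overall rejection in that row falls to 4% and 3%.

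**3. Dilution, equal prior arrest, true effect (later arrest 10% thrombolysis, 5% FlowTriever).** The true OR is (0.05/0.95)/(0.10/0.90) = 0.47.

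- Prior arrest 10% in both: 0.190 vs 0.145, OR 0.72.
- Prior arrest 20% in both: 0.280 vs 0.240, OR 0.81.

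Under the imbalance rule, prior arrest enters in only 3% to 4% of these studies, so the dilution mostly stays. Unadjusted power is 10% or less with or without prior arrest in the outcome. The damage is to the estimate.

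**4. Subgroup gate.** Reading a cell as treatment group by subgroup level, the two FlowTriever cells need 2×10 = 20 events. The plan expects 60×0.20 = 12 for the composite, and P(at least 20) = 1%. If FlowTriever risk were 40%, both FlowTriever cells would pass in 2%, 17% or 60% of studies when 20%, 30% or 50% of the events fall in the subgroup.

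**5. Subgroup timing.** This needs no arithmetic. Whether the periods in 6.7 are pooled or analysed one by one, strata based on ECMO during or after, or arrest during, are defined after treatment start. Only strata based on status before treatment are baseline subgroups.

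**The case against.** The strongest objections concern reading and size.

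- **Separate periods.** Section 5.3 records the three periods as separate items, so reporting them separately is at least as natural as pooling. The arrest item is then a wording fault with no bias. This stands as a limit: every arrest figure above depends on pooling. The SAP does not settle the reading, and a baseline comparison still sits in a list of outcomes.
- **The 28% is not the planned analysis.** The SAP plans adjusted models, and with adjustment rejection is 3% to 6% against a nominal 5%. This also stands. Inflation of false positives is small, and the 28% is an upper scenario.
- **The selection rule is assumed.** On the pooled reading prior arrest predicts the outcome by construction. If strong predictors or known confounders are always kept, it would nearly always enter the model, and both the residual bias and the dilution would largely disappear. But 5.6 tests this variable as a confounder related to both treatment and outcome, which also supports requiring imbalance. The text leaves this open.
- **Harm from the subgroups is not quantified.** This is true; only the gate has been put in numbers. The gate makes the primary-outcome analysis unlikely to run, but it does not make the result interpretable when it does.

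**Conclusion.** The concern holds and is minor. Both definitions are wrong as written: an event before treatment cannot be an outcome of treatment, and events after treatment start cannot define baseline subgroups. The first fault distorts results only if the arrest periods are pooled. How much then depends on arrest rates the SAP does not give and on a selection step it does not fix: from almost nothing if prior arrest is always in the model, to an odds ratio of 0.68 in place of 1.00 (median, when it is left out under 20% vs 10%), or 0.72 to 0.81 in place of 0.47 through dilution. The second fault applies on either reading, but at the planned 20% FlowTriever rate the primary-outcome subgroup analysis would almost never be run. The main primary analysis and the other confirmatory analyses are not touched. Table 4.2, which runs the subgroups on the primary outcome, is exploratory.

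**What to change.** - **Section 5.5.2:** define the outcome as cardiac arrest during, or within 24 h after, treatment. Keep arrest before treatment as a baseline characteristic and covariate only.
- **Section 6.7:** define the two subgroups by ECMO before treatment and cardiac arrest before treatment. Report later ECMO and arrest as outcomes or descriptively. The event gate can stay.

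This changes SAP wording only, because section 5.3 already collects each period separately. The cost is smaller subgroups, so the gate will be met even less often.
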